5.3. Operative procedure

In this study Autologous Chondrocyte Implantation (ACI) is compared with Arthroscopic Debridement (AD). All patients will undergo a diagnostic arthroscopy, and patients randomized to AD will have this procedure performed at the end of the diagnostic arthroscopy, while for the patients in the ACI group the chondrocyte implantation will take place two weeks later in a second stage operation as described below. The ACI technique is based on the technique described by Brittberg [23].

Diagnostic arthroscopy:

Three standard incisions are made (supralateral for the patella and medial and lateral for the patellar tendon). A thorough diagnostic arthroscopic examination is then done. Removal of loose bodies and other necessary intraarticular procedures are done first (meniscus, plica). The focal cartilage lesion is then measured using a standard 4-mm arthroscopic probe and ICRS graded [39, 40].

Then either arthroscopic debridement (AD) or autologous chondrocyte implantation (ACI) is done, depending on randomization.

Autologous Chondrocyte Implantation

ACI is a three stage procedure taking place at Akershus University Hospital and Oslo University Hospital (Ex-Vivo Laboratory) over a two week period.

Stage 1: Debridement and cartilage harvest.

Stage 1 includes a diagnostic arthroscopy with full inspection of the knee joint to ensure the inclusion criteria are fulfilled. Loose bodies are removed, any meniscal pathology is addressed. Inflamed synovium is debrided. The lesion is stabilized by debridement around the edges and down to the subchondral bone using a ring curette, but not through it, as described above. Cartilage biopsy is then taken from the non-weightbearing area of the medial aspect of the femoral notch. If this area does not contain enough healthy cartilage, the secondary donor site will be the non-weight bearing aspect of the lateral femoral condyle. Complications or donor site morbidity following arthroscopic harvesting of cartilage in this manner has not been described [22].

Stage 2: Chondrocyte growth in Ex Vivo Laboratory Rikshospitalet, Oslo University Hospital

The harvested cartilage is transported to the cell culture laboratory (Ex Vivo Laboratory at OUS, directed by [name]) in a sterile tube containing 0.9 % NaCl. The cells undergo mechanical mincing and antibiotic washing, and isolation of the chondrocytes by overnight collagenase digestion. The chondrocytes are then cultured for two weeks and resuspended to a treatment density of 30 million cells/ml. The cells are then transported back to Ahus for implantation.

Stage 3: Implantation of chondrocytes two weeks after initial arthroscopy.

The chondrocyte implantation is performed under general or spinal anesthesia, and a tourniquet inflated to 300 mmHg to achieve a blood-less field is applied to the upper thigh. A mini-open arthrotomy (medial or lateral depending of the location of the lesion) is performed and the lesion is assessed. The lesion is curetted down to subchondral bone, but care is taken to avoid bleeding. The surrounding cartilage is debrided to healthy tissue, exposing the lesion to bare bone. The lesion is measured and a template of sterile aluminum foil is used to model the exact shape of the lesion, overcorrecting with 1-2 millimeters.

The template is then used to cut out a matching piece of collagen sheet (ChondroGide® (Geistlich Pharma, Switzerland)) which is used to contain the cells in the defect. The flap is sutured to the lesion with 6.0 resorbable stitches and sealed with fibrin glue, leaving an opening at the upper part for injection of the cells. Saline is injected to the cavity to check for leakage, then aspirated before the cells are slowly injected using a soft catheter. The last opening is then closed with a last stitch and fibrin glue. The knee is then closed in the standard manner, taking care to close the capsule with subcutaneous resorbable sutures, before closing the skin incision with nylon sutures.

Arthroscopic Debridement

The AD group will be subjected to a diagnostic arthroscopy with a full inspection of the knee joint to ensure the inclusion criteria are fulfilled. Loose bodies are removed, any meniscal pathology is addressed. Inflamed synovium is debrided. The lesion is stabilized by debridement around the edges and down to the subchondral bone using a ring curette, but not through it. Microfracture or any other cartilage treatment will not be performed.

No intra-articular local anesthetics will be used due to the possible harmful effect on cartilage [41-43].

All the operating surgeons will receive proper training in the operative procedure before study start.

5.4. Operative procedure – blood samples for parallel study

On the day of surgery, all patients will have a 5 mL venous blood sample drawn through a standard puncture of vena cubiti in the elbow using a 22 gauge needle. The fasting blood sample will be taken after 30 minutes of bedrest, to limit the influence of preceding physical activity. The blood sample is part of the healer – nonhealer study by professor [name] at Oslo University Hospital – Rikshospitalet. For more information see Section “7.2. Parallel study: “Healer / NonHealer”

5.5. Post-operative management

The two treatment groups will receive identical postoperative care. The patients are usually admitted to the hospital for up to 4 days. No intravenous prophylactic antibiotics are given, anti-thrombotic prophylaxis is given only when there is a risk of thromboembolic disease (such as previous deep vein thrombosis or pulmonary embolus, protein C or S deficiency, Leiden V mutation and use of contraceptive pills). All patients will be given a sick leave up to 2 weeks after the operation.

If a patient experiences complications during treatment such as wound infections, catching or locking etc. the patient will receive medical attention and follow-up according to the problem.

5.6. Rehabilitation protocol

The two treatment groups will receive identical rehabilitation protocol according to a modification of Wondrasch et al [17]. The study will have a designated study physiotherapist, [name], leading the rehabilitation program along with the patients local physiotherapist.

Rehabilitation phases	Physiotherapy and activities	Objectives	Criteria for progression to next phase
Phase1: Accomodation	Education/coaching Ice, elevation and compression Isometric exercises Range of motion Gait training (no weight-bearing for two weeks)	Reduce pain and swelling Normalize range of motion Regain quadriceps control	No pain & swelling during activities of daily living (ADL) Flexion 90° Normalized quadriceps activity while walking (clinical evaluation by the physical therapist)
Phase2: Rehabilitation	Stationary bike cycling Progressive knee and hip resistance training Neuromuscular training	Recovery of full range of motion Normalize muscle strength Dynamic joint stability during ADL	Full range of motion No pain or swelling during and after training sessions Equally distributed weight on the lower limbs during weight-bearing exercises with no shift of the trunk (visually assessed by the physical therapist) Ability to stand on 1 limb on a flat surface for at least 10 seconds
Phase 3: Return to activity	Knee and hip resistance training Neuromuscular training Cardiovascular training	Recovery of strength and neuromuscular control Return to activity/sport	Return to sport based on individual assessment

Rehabilitation protocol (identical for both groups).

The patients are admitted to the hospital for 2-4 days. The patients are seen by a physiotherapist and the surgeon day 1 after surgery to be instructed in range of motion

exercises and restrictions according to Phase 1. The patient is seen within two weeks by a local physiotherapist who has received information about the rehabilitation program, and who will follow the patient through the program, supervised by the Project Physiotherapist ([name]).

The rehabilitation program is an active rehabilitation and education program divided into 3 phases: accommodation (1), rehabilitation (2) and return to activity (3). During the rehabilitation program the physical therapist focuses on explaining why the exercises are important and how the exercises should be performed and adjusted based on pain response and other symptoms. The rehabilitation program consists primarily of cardiovascular and knee/hip progressive resistance and neuromuscular training, including balance and plyometric exercises. The local physical therapist receive information about the rehabilitation program, including what kind of exercises the patients should perform.

To monitor the adherence to the rehabilitation program, all patients are asked to use training diaries to provide information about frequency, type of exercise, load progression and number of repetitions. In addition, the patients are asked to respond every second week to an online survey, with the questions; 1. Have you been to a supervised physical therapy session during the last two weeks?, 2. How many physical therapy sessions did you attend during the last two weeks?, 3. What kind of training/exercises have you performed during the physical therapy sessions?, and 4. What kind of activities have you performed during the last two weeks? All questions are followed by several predefined answers (closed answers), but also open answers are included to make comments if required. The online survey will continue as long as the patient is under the care of a physiotherapist, while the training diary will be continued to the end of the project (24 months) to estimate the amount of home exercise performed by the patient.

Phase 1 - accomodation:

Inpatient rehabilitation consists of placing the leg in a Continuous Passive Motion (CPM) machine within the range as tolerated due to pain and swelling, aiming to achieve 30-70° day 1 after surgery. The patients should use the machine for 6-8 hours every 24 hours. The physical therapist instructs the patients in exercises such as active dorsiflexion/ plantar flexion of the ankle to encourage lower extremity circulation and isometric contraction of the quadriceps, hamstrings, and gluteal musculature to maintain muscle tone and minimize muscle loss. This also includes abduction exercises for the hip. The patients remain non-weight bearing for two weeks, but are allowed touch-down weight-bearing (the foot or toes may touch the floor, but not support any weight) through the affected limb using crutches.

When discharged from the hospital, the patients are encouraged to continue range of motion exercises; flexion/extension of the knee 500 repetitions three times a day. In this phase, 2 to 3 supervised physical therapy sessions are scheduled for each patient. Interventions such as ice, compression, electrical muscle stimulation, muscle activation of the quadriceps, hamstrings, gastrocnemius and gluteal muscles and gait training is included. Swimming is allowed when the wounds are healed.

After two weeks, protected weight-bearing is carefully introduced within the pain threshold and gradually increased up to full weight-bearing (continues into phase 2). Crutches are used until the patient walks normal without limping.

Phase 2 - Rehabilitation:

The patients attends 2 or more supervised physical therapy sessions per week, in addition they perform 1 to 2 unsupervised training sessions per week. Cardiovascular training on a stationary bike and progressive knee and hip resistance training and neuromuscular training are performed in this phase. All strengthening exercises are performed with both the injured and uninjured limbs. When full weight-bearing is achieved, long distance walking with increasing distances is encouraged and cross-country skiing can be allowed.

Phase 3 – Return to activity/sport:

This phase is individualized according to the goals for each patient. The patients attend 1 or more supervised sessions per week, in addition they perform resistance training for a minimum of 2 and a maximum of 4 sessions per week. Cardiovascular and neuromuscular training can be performed daily. Where a return to sport is planned, it is important that sport-specific activities are included as functional progressions within the rehabilitation program.

6. VARIABLES

6.1. Demographics

Demographics to be collected at inclusion is age, gender, height (cm), weight (kg), BMI, injury mechanism (if any), previous medical history, current medication, smoking, social status, work status and nationality.

6.2. Primary endpoint

The Knee Injury and Osteoarthritis Outcome Score (KOOS) is a patient reported outcome measure validated to use in cartilage research studies and will enable comparison of our results with other reports. It assesses five domains; pain, symptoms, activity of daily living,

sport and recreational function and knee-related quality of life [44]. KOOS knee-related quality of life (QoL) subscore is the primary endpoint, where the primary aim is the difference in KOOS QoL subscore in the ACI group compared to the AD group at 2 years follow up. There will not be any interim analysis before 2 years follow up.

6.3. Secondary endpoints

A combination of self-explanatory questionnaires, clinical parameters, clinical hop tests and radiographs and Magnetic Resonance Imaging (MRI) will be used as secondary endpoints. The secondary aims will be the difference between the two treatment groups and within the group at predefined times as described below. The secondary aims are:

- KOOS score: all subscores except the knee-related QoL subscore which is the primary aim.
- Tegner score; To evaluate the level of physical activity.
- Lysholm score; A condition-specific outcome score containing eight domains; limp, locking, pain, stair-climbing, use of support, instability, swelling and squatting.
- EQ-5D; A generic measure of health status that provides a simple descriptive profile used in the clinical evaluation of health care. EQ-5D is also widely used by clinical researchers and recommended for use in cost-effectiveness analyses by the Washington Panel on Cost Effectiveness in Health and Medicine [45] and by the International Society for Pharmacoeconomics and Outcomes Research (ISPOR) task force on good clinical practices: Randomized Clinical Trial-Cost-Effectiveness Analysis (RCT-CEA) [46].
- Visual analogue scale (VAS); A visual analogue scale for pain, where 0 represents no pain and 10 represents the worst pain imaginable.
- Range of motion (ROM) will be measured with a goniometer
- Costs; resource use related to the intervention, medication, rehabilitation, use of health care services and production loss.
- The patients will also provide information about work (return to work) physical activity and return to sport.

All outcome questionnaires will be completed by the patients before surgery (pre-operative or baseline values) and at the designated research follow-up appointments at 3 (± 2 weeks), 6 (± 4 weeks), 12 (± 6 weeks), and 24 (± 8 weeks) months.

At 24 months follow up, there will be 3 additional elements consisting of:

- Standing x-rays to evaluate any development of osteoarthritis.
- Magnetic Resonance Imaging (MRI); assessing the quality of the cartilage tissue, using a specific cartilageMRI technique, to assess the healing of the defect.
- A hop test, validated and described previously by Noyes, to assess clinical function [47].

We will also invite patients to attend a 5 year and 10 year follow up appointment. During these late controls, all the primary and secondary outcomes will be assessed for as described above.

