8. SECONDARY PROJECTS

8.1. Cost-effectiveness analysis

In addition to the prospective randomized trial, we will also conduct a treatment-cost analysis. By recording the cost of each treatment, need of sick leaves, cost of additional doctor's appointments and repeated surgery due to recurrence or complications, we will estimate the cost effectiveness and not only the functional results. This provides the necessary economic frame of reference from which to resolve treatment recommendations.

To assess the cost-effectiveness of the two treatment we need to estimate both health outcome and costs. The health outcome will be measured by means of EQ-5D, while costs will include costs in the health care sector and production loss. To estimate costs, we will include the cost of the interventions, which includes the use of other health care services (home care services, rehabilitation and institution) which will be registered for both groups. Standard methods in economic evaluation will be applied, and cost-effectiveness will be calculated by means of the incremental cost-effectiveness ratio, defined by the cost per incremental QALY. Further uncertainty will be displayed by applying the bootstrap method with 1000 replications to illustrate the variation in the patient population with regard to incremental health gain and cost.

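### No EQ-5D is taken between the pre-operative measurement and 3 months, so the QALY difference probably favours ACI by leaving out short-term loss from its second operation

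*Protocol*

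**What the plan says.** Section 6.3 of the protocol states: "All outcome questionnaires will be completed by the patients before surgery (pre-operative or baseline values) and at the designated research follow-up appointments at 3", and goes on to 6, 12 and 24 months. The Study Activities table in the synopsis agrees and has no questionnaire between inclusion and 3 months.

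Section 8.1 bases the economic evaluation on this instrument: "The health outcome will be measured by means of EQ-5D". It continues: "cost-effectiveness will be calculated by means of the incremental cost-effectiveness ratio, defined by the cost per incremental QALY". Sections 6.3 and 8.1 count the cost of the interventions, use of health services and production loss. The rule that turns EQ-5D scores into QALYs is not given.

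The arms differ in their surgery (section 5.3). In the control arm, "patients randomized to AD will have this procedure performed at the end of the diagnostic arthroscopy". In the other arm, "the chondrocyte implantation will take place two weeks later in a second stage operation", through a mini-open arthrotomy. Section 5.6 says: "The patients remain non-weight bearing for two weeks". It does not say which of the two ACI operations starts that period.

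One data stream already covers early follow-up. Under section 5.6, "the patients are asked to respond every second week to an online survey". Its four questions concern physiotherapy and activities; EQ-5D is not among them.

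**The concern.** A QALY over two years is normally the area under the EQ-5D curve, with straight lines between measurements. From the pre-operative value to 3 months that line passes over one surgical recovery in AD and two in ACI. If an operation lowers EQ-5D for some weeks, the loss is missed in both arms, and probably more of it in ACI.

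The cost side has no matching gap. Cells, membrane, the second operation and production loss are all recorded. The second operation therefore raises the numerator of the cost per QALY, while its short-term health loss does not lower the denominator. If ACI shows a QALY gain, the ratio comes out too low.

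The bootstrap planned in section 8.1 describes sampling variation and would not reveal a gap common to every patient. An analysis plan could specify the QALY rule, but it could not recover measurements that were never taken.

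**Working it through.** The protocol states no utility, QALY or cost-effectiveness figure, so there is none to reproduce.

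**Inputs from the protocol**
- EQ-5D before surgery and at 3, 6, 12 and 24 months (section 6.3).
- One operation in AD; two in ACI, two weeks apart (section 5.3).
- Extra ACI cost: 35,000 NOK for cells + 7,500 NOK for the membrane = 42,500 NOK (section 13.1). Other cost differences are left out.

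**Assumptions, not in the protocol**
- Utility 0.60 before surgery and 0.70 at 3 months (13 weeks) in both arms.
- Utility 0.40 in both arms in weeks 0 to 2.
- In ACI, utility 0.40, 0.30 or 0.20 in weeks 2 to 4.
- Linear recovery to 0.70 at week 13, from week 2 in AD and week 4 in ACI.
- A reported gain of 0.10 QALY for ACI over two years.

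**Step 1: area as the planned visits would give it.** Both arms: (0.60 + 0.70)/2 × 13/52 = 0.1625 QALY, so the difference over this interval is zero.

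**Step 2: area with the dips, AD.** 0.40 × 2/52 + (0.40 + 0.70)/2 × 11/52 = 0.0154 + 0.1163 = 0.1317 QALY.

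**Step 3: area with the dips, ACI.** With utility d in weeks 2 to 4, the area is 0.40 × 2/52 + d × 2/52 + (d + 0.70)/2 × 9/52. The missed difference is 0.1317 minus this area. The corrected cost per QALY is 42,500/(0.10 − missed difference), against 42,500/0.10 = 425,000 NOK as planned.

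| d | ACI area | Missed difference | NOK per QALY |
|---|---|---|---|
| 0.40 | 0.1260 | 0.0058 | about 451,000 |
| 0.30 | 0.1135 | 0.0183 | about 520,000 |
| 0.20 | 0.1010 | 0.0308 | about 614,000 |

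**Step 4: cruder check with other assumptions.** Missed difference = loss × extra ACI recovery weeks/52. A loss of 0.1 for 2 extra weeks gives 0.1 × 2/52 = 0.004; a loss of 0.4 for 4 extra weeks gives 0.4 × 4/52 = 0.031. Assume an EQ-5D advantage g for ACI at 12 and 24 months, half of it at 6 months and none at 3 months. For g = 0.05, the trapezoid gain is 0.5 × 0.025 × 0.25 + (0.025 + 0.05)/2 × 0.5 + 0.05 × 1 = 0.072 QALY.

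| g | Gain as planned | NOK per QALY as planned | After subtracting 0.004 to 0.031 |
|---|---|---|---|
| 0.10 | 0.144 | about 296,000 | about 304,000 to 376,000 |
| 0.05 | 0.072 | about 591,000 | about 625,000 to 1,033,000 |
| 0.02 | 0.029 | about 1.48 million | from about 1.71 million; at the far end the gain is −0.002 |

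The omission matters little if the benefit of ACI is large and a good deal if it is modest.

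**Step 5: the offset.** Suppose ACI is still at 0.65 at the 3-month visit, with d = 0.40. The planned ACI area is (0.60 + 0.65)/2 × 13/52 = 0.1563. The area with the dip is 0.40 × 4/52 + (0.40 + 0.65)/2 × 9/52 = 0.1216. ACI misses 0.0346 and AD misses 0.1625 − 0.1317 = 0.0308, so the difference falls from 0.0058 to 0.0038 QALY.

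**The case against.** Four points on the other side deserve weight.

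- **The direction is likely, not certain.** The protocol does not say whether the ACI visit clock starts at the arthroscopy or at the implantation. If at the arthroscopy, the 3-month visit falls about 11 weeks after implantation in ACI, against 13 weeks after surgery in AD. A residual ACI deficit would then be measured and interpolated back (step 5). It would also be carried forward to 6 months: a deficit of 0.05 contributes 0.5 × 0.05 × 0.25 = 0.006 QALY there, which overstates the ACI loss if recovery is faster than linear. At the low end this could cancel the omission. This stands.
- **The utilities are assumed.** This also stands. The document supports the mechanism but not its size. A cost per QALY that is too low further presupposes a positive ACI gain, which the two-sided hypothesis in section 7.1 leaves open.
- **The analysis is secondary.** Section 8 presents it as a secondary project, and KOOS QoL at two years is untouched. This limits the importance of the point, though section 8.1 does intend the result to inform treatment recommendations.
- **The QALY rule may be in an analysis plan.** It may, but the measurement times are fixed here.

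Three stronger readings are tempting, and the document does not support them. A reader might infer that EQ-5D is not taken at all until 3 months; section 6.3 gives a pre-operative value. A reader might infer that each ACI operation has its own two-week non-weight-bearing period; section 5.6 states one period and does not tie it to either operation. A reader might also set ACI below AD from week 0, at 0.20 for four weeks, and reach 0.038 QALY and 691,000 NOK. But section 5.3 describes the first ACI stage and AD in nearly the same terms, apart from the cartilage biopsy, so a deeper ACI loss in weeks 0 to 2 has no basis there.

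**Conclusion.** The point holds as a limited one. The EQ-5D schedule leaves unmeasured the interval in which the arms differ most in surgery, while the cost side records that difference. The incremental QALY is therefore likely to be biased in favour of ACI, by an amount the document cannot give. Under the assumptions of steps 1 to 3 the missed difference is about 0.006 to 0.031 QALY. For a reported gain of 0.10 QALY and 42,500 NOK, the cost per QALY rises by about 6% to 44% over 425,000 NOK. A residual ACI deficit at 3 months would shrink this. The reason to act is that the correction is cheap and the missing data cannot be recovered later.

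**What to change.** - Add EQ-5D to the two-weekly online survey for the first 12 weeks from the index arthroscopy, which is also the time of randomisation, in both arms. That is up to six completions per patient.
- State that the survey starts on that date in both arms. Section 5.6 gives no start date and ties the survey's duration to physiotherapy care, so as written it may not cover the weeks between the two ACI operations.
- Compute QALYs from that common origin in both arms, using the survey points plus the 3, 6, 12 and 24 month visits.

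The cost is amendment wording and a short questionnaire in a survey already planned, with no new visit. The drawbacks are a small burden on patients, some missing responses, and online EQ-5D alongside the paper forms described in section 11. The resulting cost per QALY may be less favourable to ACI.
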